## Protocol Body

E7070 Amendment 6 Final 11-15-2013.doc

**Title: A Phase 2, Open-label Study of E7070, Idarubicin and Cytarabine in Patients with Relapsed or Refractory Acute Myeloid Leukemia and High-Risk Myelodysplastic Syndromes.**

**Principal Investigator:** [name]

**Protocol Number:** 2009-0570

**Date of Protocol:** May 25, 2010

**Amendment #1:** February 9, 2011

**Amendment #2:** July 11, 2012

**Amendment #3:** October 3, 2012

**Amendment #4:** March 14, 2013

**Amendment #5:** June 21, 2013

**Amendment #6:** November 15, 2013

|                                       |   |
|---------------------------------------|---|
| TITLE                          | A Phase 2, Open-label Study of E7070, Idarubicin and Cytarabine in Patients with Relapsed or Refractory Acute Myeloid Leukemia and High-Risk Myelodysplastic Syndromes.  |
| INVESTIGATORS / TRIAL LOCATION | [name].
University of Texas M.D. Anderson Cancer Center
Dept. of Leukemia,
[name]
[name]  |
| SUPPORTER                      | Eisai, Inc.   |
| STUDY OBJECTIVES               | 
Primary objective:
 
 
1. To assess the complete response (CR) and CR with incomplete platelet recovery (CRp) rates with combination therapy of E7070, idarubicin and cytarabine in patients with relapsed or refractory acute myeloid leukemia (AML) or high-risk myelodysplastic syndromes (HRMDS)
 
2. To determine the safety and toxicity profile of combination therapy with combination therapy of E7070, idarubicin and cytarabine in patients with relapsed or refractory AML or HRMDS.
 
 
Secondary objectives:
To determine the:
 
 
1. duration of response;
 
2. disease-free survival; and
 
3. overall survival
 
  |
| STUDY DESIGN                   | Phase 2   |
| STUDY POPULATION               | 
Eligibility criteria:
 Inclusion:
 
 
1. All patients with histologically or cytologically confirmed relapsed or refractory AML [except acute promyelocytic leukemia], or HRMDS (Int-2 high risk by IPSS or >10% blasts in marrow).
 
2. Patients must be 18 years or older.
 
3. Patients must have a performance status of 0-2 (Zubrod scale).
 
4. Patients must have adequate renal function (serum creatinine <math>\leq</math> 1.3 mg/dL and/or creatinine clearance <math>></math> 40 mL/min). Patients with renal dysfunction due to organ infiltration by disease may be eligible after discussion with the P.I., (up to creatinine <math>\leq</math> 2.0) and appropriate dose adjustments will be considered.
 
5. Patients must have adequate hepatic function (bilirubin <math>\leq</math> 2.0 mg/dl; SGOT or SGPT <math>\leq</math> 3X the ULN for the reference lab unless due to leukemia or congenital hemolytic disorder or bilirubin) excretion disorder. Patients with hepatic dysfunction (SGOT/SGPT up to <math>\leq</math> 5X ULN) due to organ infiltration by disease may be eligible after discussion with the P.I., and appropriate dose adjustments will be considered.
 
6. Patients must have normal cardiac ejection fraction.
 
7. QTc interval <math>\leq</math> 480 msec.
 
8. Patients must sign an informed consent form indicating that they are aware of the investigational nature of this study, in
 
 |

|  |   |
|--|---|
|  | 
keeping with the policies of the hospital.
 
9. Female patients must not be pregnant or lactating. Female patients of childbearing potential (including those <1 year post-menopausal) and male patients must agree to use contraception.
 
Exclusion:
 
 
1. Patients must not have untreated or uncontrolled life-threatening infection.
 
2. Patients must not have received chemotherapy and/or radiation therapy within 2 weeks. Hydroxyurea is allowed up to 48 hours prior to starting therapy in the setting of rapidly proliferating disease. For details of allowance of hydroxyurea use after the start of study drug, please refer to section VI.
 
3. Patients must not have received an investigational anti-cancer drug within two weeks of E7070 administration.
 
4. Any other medical condition, including mental illness or substance abuse, deemed by the Investigator to be likely to interfere with a patient's ability to sign informed consent or cooperate and participate in the study or with the interpretation of the results.
 
 |
| TOTAL EXPECTED NUMBER OF PATIENTS | Up to 40  |
| STUDY DRUGS                       | 
E7070
 
Idarubicin
 
Cytarabine
 
Dexamethasone
   |
| ROUTE OF ADMINISTRATION           | IV  |
| DOSE REGIMEN                      | 
E7070 400 mg/m^2 intravenously (IV) approximately over 1 hour on day 1 and day 8:
 
Idarubicin 8 mg/m^2 IV approximately over 1 hour daily x 3 (days 9-11)
 
Cytarabine 1.0 g/m^2 IV approximately over 24 hours daily on day 9-12 (age <60 years) or days 9-11 (age ≥ 60 years).
 
Dexamethasone 10 mg IV daily for 3-4 days with cytarabine (Duration is approximately 28 days).
   |
| EVALUATION CRITERIA               | Toxicity will be evaluated using the National Cancer Institute (NCI) Version 4.0 criteria.  |
| DURATION OF STUDY PERIOD          | Patients will continue on study until death, disease progression, unacceptable toxicity, patient refusal, or withdrawal from study.   |

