**VII PRETREATMENT EVALUATION (within 7 days of start of study drug except where noted)**

- History and Physical Examination to include vital signs and weight.
- CBC with differential platelets, glucose, total protein, albumin, electrolytes [sodium, potassium, chloride, CO2], calcium, phosphorus, magnesium, uric acid, bilirubin (total, direct), SGPT (ALT) or SGOT (AST), alkaline phosphatase, lactate dehydrogenase, creatinine, blood urea nitrogen.
- Record all concomitant medications and baseline adverse events.
- Bone marrow aspirate and/or biopsy (within one month), and cytogenetics, unless these tests were done within 3 months.
- Chest x-ray (PA and lateral) [at or within one month of screening].
- Electrocardiogram [at or within 1 month of screening].
- Evaluation of cardiac ejection fraction (MUGA or ECHO) (at or within 1 month of screening).

- Urine or blood pregnancy test for women of childbearing potential (within 7 days prior to day 1).
- ECOG assessment.

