## **VIII. EVALUATION DURING STUDY**

- CBC, differential (if WBC >  $10^9/L$ ), every 4-7 days during Cycle 1 and every 1 to 4 weeks during Cycle 2.
- Record all concomitant medications and adverse events: continuously during study.
- Disease assessment: Cycle 1, Day 28 (+/- 3 days)
- Electrocardiogram on Day 2 (+/- 1 day) and Day 8 (+/- 2 days) of Cycle 1 done at least 1 hour after completion of E7070 infusion.
- Bone marrow aspiration on day 28 (+/- 3 days) and as indicated at the discretion of the treating physician until documentation of response. Bone marrow examinations may be omitted in patients where there is clear evidence of active disease (e.g., increasing blasts in peripheral blood).
- Creatinine, total bilirubin, electrolytes, AST and/or ALT once every week during induction Cycle 1, then every 2-4 weeks during Cycle 2.
- Safety lab assessments (CBC, differential, platelets, creatinine, total bilirubin, electrolytes, AST and/or ALT) can be performed by local physician, see Section X.

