 To include glucose, total protein, albumin, electrolytes [sodium, potassium, chloride, CO2], calcium, phosphorus, magnesium, uric acid, bilirubin (total, direct), SGPT (ALT) or SGOT (AST), alkaline phosphatase, lactate dehydrogenase, creatinine, blood urea nitrogen will be performed at least weekly.

 Creatinine, total bilirubin, electrolytes, AST and/or ALT once every week during Cycle 1, then every 2-4 weeks during Cycles 2-3.

 Within one month, to include cytogenetics, unless these tests were done within 3 months.

 And as indicated until documentation of response. Bone marrow examinations may be omitted in patients where there is clear evidence of active disease (e.g., increasing blasts in peripheral blood)

 At or within 1 month of screening

 Done at least 1 hour after completion of E7070 infusion if EKG is done on the day of the E7070 infusion day

 For women of childbearing potential within 7 days prior to day 1

 If patient is found to be CR, CRp, PR or marrow clearance of blasts, may receive up to 2 additional cycles of E7070 in combination with chemotherapy

 To include vital signs and weight

 Approximately every 28 days to 2 additional cycles

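### The only ECG required before the first E7070 infusion may date from up to a month before screening, so the QTc entry limit need not hold on the day of dosing

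*Combined protocol and SAP*

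**What the plan says.** Inclusion 7, in the Synopsis and again in Section V, requires "QTc interval \leq 480 msec". It attaches no date to the measurement.

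The timing comes from Section VII, whose heading sets a default: "PRETREATMENT EVALUATION (within 7 days of start of study drug except where noted". The ECG is one of the noted exceptions: "Electrocardiogram [at or within 1 month of screening". Footnote 7 to the Section XII schedule repeats it ("At or within 1 month of screening") for the chest x-ray, the ECG and the ejection fraction. The protocol does not define screening as a particular day.

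On treatment, Section VIII schedules "Electrocardiogram on Day 2 (+/- 1 day) and Day 8 (+/- 2 days) of Cycle 1", at least 1 hour after the E7070 infusion ends. Footnote 8 applies that delay only to a tracing made on an infusion day: "Done at least 1 hour after completion of E7070 infusion if EKG is done on the day of the E7070 infusion day".

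On earlier treatment, Exclusion 2 states "Patients must not have received chemotherapy and/or radiation therapy within 2 weeks", and Exclusion 3 sets the same 2-week limit for investigational anti-cancer drugs. Hydroxyurea has its own rule: "Hydroxyurea is allowed up to 48 hours prior to starting therapy in the setting of rapidly proliferating disease".

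**The concern.** An entry limit on QTc protects a patient only if it describes that patient when dosing begins. Here the qualifying tracing can be a month old or more, and it can predate another course of chemotherapy or an investigational drug. A patient known to exceed 480 msec is ineligible, but nothing obliges anyone to look again before E7070 is first given. Creatinine and bilirubin also decide eligibility, and both must be measured within 7 days.

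There is a second, smaller consequence. If QTc is long on Day 2 or Day 8, the investigator may have no recent pre-dose tracing to compare with when judging whether E7070 is responsible. Section XV bases causality partly on timing, and relatedness to study drug is part of the toxic-event definition behind the Section XX stopping rule.

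**Working it through.** The plan gives no figure to reproduce, so the check is calendar arithmetic on its windows.

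**Does any scheduled ECG fall between the qualifying one and the first infusion?**

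- The earliest day for the first on-study ECG is Day 2 − 1 = Day 1, which is an infusion day. Section VIII and footnote 8 both then place the tracing at least 1 hour after the infusion.
- The earliest day for the second is Day 8 − 2 = Day 6, after the first infusion.
- Neither can precede the first dose, and no other section calls for a repeat ECG or a confirmation of QTc.

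**Inputs**

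- M, the ECG window before screening: 1 month, taken as 28–31 days (Section VII; footnote 7).
- s, the days from screening to Day 1: not defined. Assumed to run from 0 to 7, the length of the default pretreatment window.
- W, the washout: 14 days (Exclusions 2 and 3). Exclusion 2 does not say where the 2 weeks are counted from; Day 1 is assumed.

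**Formulas**

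- Oldest permitted ECG at first dose: A = M + s
- Longest interval in which other treatment could follow that ECG with the patient still eligible: G = A − W

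**Results**

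| Screening day | A (days) | G (days) |
|---|---|---|
| Day 1 (s = 0) | 28 to 31 | 28 − 14 = 14 to 31 − 14 = 17 |
| Day -7 (s = 7) | 28 + 7 = 35 to 31 + 7 = 38 | 35 − 14 = 21 to 38 − 14 = 24 |

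If the washout is counted back from screening instead, s drops out and G = M − W = 14 to 17 days whichever day screening falls on. The longest permitted interval is therefore at least 14 days under every reading considered.

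**With the ECG in the 7-day window**

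A is at most 7 days. Because 7 is less than 14, barred treatment cannot follow the ECG, and G = 0. Hydroxyurea is the exception, since it may continue until 48 hours before the start.

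**The case against.** The strongest reply is that the exception is deliberate and coherent. Section VII announces exceptions, and the chest x-ray and ejection fraction share this one. Nor do the documents show harm: the E7070 sections do not mention QT, and the ECG changes listed for idarubicin do not include QTc prolongation. This stands in part, because the size of any QTc risk cannot be judged from the documents. It does not remove the point. The plan itself makes QTc an entry limit and times ECGs around E7070, so the only question is whether the limit is checked when it matters.

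A second reply is that there are other safeguards. Physical examination, electrolytes (with calcium and magnesium), concomitant medications and baseline adverse events are all required within 7 days, and an investigator may order an extra ECG. These can prompt a repeat tracing, but none measures QTc and none makes a repeat mandatory.

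A third is that the gap covers only the first infusion. That is correct. The Day 2 ECG precedes the Day 8 infusion, and idarubicin and cytarabine start on Day 9. The point is limited accordingly.

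A fourth is that ejection fraction is also an entry criterion with the same window, and the protocol says myocardial toxicity is more common after earlier anthracyclines. The argument about an outdated test applies there too. The ECG is singled out because it is the only footnote 7 test repeated on treatment, so a recent tracing also serves as the comparator. The case for a newer ejection fraction is not made here.

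**Conclusion.** The point holds as an optional, low-cost improvement. Inclusion 7 can be satisfied by an ECG 28–31 days old at first dose (screening on Day 1) or 35–38 days old (screening on Day -7). That leaves up to 14–17 or 21–24 days in which other chemotherapy or an investigational drug could follow it. No scheduled ECG would reveal a QTc above 480 msec before the first E7070 infusion.

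The figures assume a month of 28–31 days, screening between Day -7 and Day 1, and a washout counted back from Day 1; counting it from screening gives 14–17 days throughout. They describe what the plan permits, not what will happen: an older ECG is allowed, not required, and the number of patients affected cannot be derived.

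The plan specifies no QTc baseline or change-from-baseline analysis, and Section XX tabulates worst grade per patient for selected adverse events and laboratory measurements. No planned analysis is invalidated.

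**What to change.** Delete the 1-month exception from the ECG line in Section VII and remove the footnote 7 marker from the ECG row of the Section XII schedule. The existing window of 7 days before start of study drug then applies, with the tracing taken before the first E7070 infusion. Leave footnote 7 in place for the chest x-ray and ejection fraction.

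No separate clause on earlier treatment is needed, because 7 days lies inside the 2-week washout. The hydroxyurea allowance can stay as it is.

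The cost is one line of text and one footnote marker. The number of scheduled ECGs does not change. The one drawback is that a patient who has only an older ECG must have it repeated at screening.

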## I. OBJECTIVES

### Primary Objectives

1. To assess the complete response (CR) and CR with incomplete platelet recovery (CRp) rates with combination therapy of E7070, idarubicin and cytarabine in patients with relapsed or refractory acute myeloid leukemia (AML) or high-risk myelodysplastic syndromes (HRMDS), and.
2. To determine the safety and toxicity profile of combination therapy with combination therapy of E7070, idarubicin and cytarabine in patients with relapsed or refractory AML or HRMDS.

### Secondary Objectives

Determine the duration of response, disease-free survival, and overall survival.

## II. BACKGROUND

### *The Disease*

The cure rates for patients with relapsed or refractory hematological malignancies are dismal. Therefore, new agents need to be identified, tested in clinical trials, and incorporated into effective regimens to improve the prognosis of these patients. This study is designed for patients with relapsed/refractory AML and HRMDS whose duration of first CR was less than 1 year. Once front-line therapy fails, patients' therapeutic options are limited. This population of patients with disease that has relapsed or is refractory to established frontline therapies has response rates of less than 10% to 20%. Even if a small proportion of these patients achieve a remission, the remissions are short lasting.

### *Rationale for Proposed Therapy*

#### **Idarubicin and Cytarabine**

While a combination of an anthracycline (daunorubicin or idarubicin) and cytarabine is standard 'induction' regimen for patients with newly diagnosed AML, the 'best' salvage regimen for patients with relapsed disease is unclear. While patients with initial CR duration of over 1 year clearly benefit from high-dose cytarabine (HDAC) based regimens, the probability of achieving a second CR for patients with shorter first CR duration is very low. Cytogenetics, age, failure of prior salvage attempts add to the poor outcome of these patients. Investigational agents alone or in combination with traditional chemotherapy in clinical trials should be the most appropriate approach for these patients.

## III. BACKGROUND DRUG INFORMATION

### **A. E7070**

(Information detailed in Investigator's Brochure: all references in parentheses are Eisai reports outlined in Investigator's Brochure)

E7070 is a sulfonamide anticancer agent that was selected out by G1 cell-cycle arrest effect in murine leukemia P388 cells and antitumor effect in human tumor xenograft models in mice. E7070 induces G1 cell-cycle arrest and delay in G1/S transition in both P388 cells (P1&P2)

and the colorectal cancer CRC cell line HCT116 (P3). Cell cycle arrest in these cases is followed by induction of apoptosis at higher dose (P2). These effects of E7070 on cell cycle progression and apoptosis were found to be time-dependent (P2).

Gene expression analysis using high-density oligonucleotide microarrays has revealed that E7070 treatment causes characteristic repression of subsets of genes involved in redox metabolism, cell cycle control, immune response, and signal transduction (P5). A significant reduction in DNA topoisomerase II alpha and glutathione synthetase transcripts may provide a molecular basis for combination therapy with irinotecan (CPT-11) and platinum agents, respectively.

Proteomic studies using E7070-based affinity matrixes have identified cytosolic malate dehydrogenase (cMDH) as a specific binding protein of E7070. cMDH is a critical metabolic enzyme involved in the malate-aspartate shuttle, gluconeogenesis, and glycolysis. It catalyses the reversible conversion of oxaloacetate to malate using nicotinamide adenine dinucleotides (NAD and NADH) as cofactors. The core structure of E7070 competes with NADH in binding to cMDH at a physiologically relevant concentration (P6). It has yet to be demonstrated that this binding property is a prerequisite for the antitumor activity of E7070.

### **Potential interactions with other medications**

Human liver microsomal studies have shown that there is potential for CYP450 (CYP2C9, 2C19 and 3A4) inhibition by indisulam. As a consequence, there is a hypothetical chance of an interaction between indisulam and a number of drugs. Some drugs with which this interaction may be observed have a relatively narrow therapeutic index and so are of potential concern. The most important of these are listed below:

- oral anticoagulants
- terfenadine, cisapride, cyclosporin, tacrolimus
- theophylline
- diazepam
- sulphonylurea anti-diabetics
- phenytoin and carbamazepine.

There have been reports of drug interactions between E7070 and oral anticoagulants. Three patients from the Phase I program who were receiving chronic therapy with the oral anticoagulant acenocoumarol experienced bleeding and/or a further prolongation of the prothrombin time following treatment with E7070 at a dose of 700 mg/m^2 given as a 1-hour infusion. A pharmacokinetic study was performed to investigate this interaction further. The results indicate that E7070 may primarily interact with acenocoumarol by reducing its systemic clearance. Displacement of acenocoumarol's plasma protein binding by E7070 may also occur, but to a minor extent. In view of these findings, clinicians are advised to exercise caution during the introduction and after the withdrawal of E7070 therapy in patients stabilized on oral anticoagulation.

**Pre-clinical** work outlined below indicates synergy of E7070 with traditional chemotherapeutic agents.

### **E7070 Dosing**

Section 5.4.1 Table 34 in the Investigator's Brochure is the summary for recommended phase 2 doses for single agent E7070 and for the weekly schedule, 400 mg/m^2 weekly times four is

the recommended dose. In our proposed study, the dose of E7070 is scheduled at 400 mg/m^2 weekly times two to allow for the addition of chemotherapy and to avoid undue toxicity with the combination.

Moreover, in a phase 2 study (E7070-E044-214) combining E7070 with chemotherapy, the dose of E7070 was 400 mg/m^2 with irinotecan 125 mg/m^2 on days 1 and 8 in a 21 day cycle (Table 5.5.5 Page 93 of Investigator Brochure) and this was tolerated with acceptable level of toxicity (diarrhea, vomiting, cytopenias being most frequent toxicities).

These data has been used to arrive at the proposed doses in the current protocol.

The doses of idarubicin and cytarabine to be administered are lower than the usual 12mg and 1.5 gram per meter squared that is usually used, to avoid undue toxicity when combined with E7070.

## **C. Idarubicin**

Idarubicin is commercially available and will not be supplied for this protocol. Please see package insert for further information.

Synonyms: 4-Demethoxydaunorubicin; 4-DMDR, Idarubicin Hydrochloride, IDR: IMI 30; NSC-256439, SC 33428, Idamycin

Use: Treatment of acute leukemias (AML, ANLL, ALL), accelerated phase or blast crisis of chronic myelogenous leukemia (CML), breast cancer

Contraindications: Hypersensitivity to idarubicin, other anthracyclines, or any component of the formulation; bilirubin >5 mg/dl; pregnancy

Warnings/Precautions: The U.S. FDA currently recommends that procedures for proper handling and disposal of antineoplastic agents be considered. Can cause myocardial toxicity and is more common in patients who have previously received anthracyclines or have preexisting cardiac disease; reduce dose in patients with impaired hepatic function.

Adverse Reactions: >10%: Cardiovascular: Transient EKG abnormalities (supraventricular tachycardia, S-T wave changes, atrial or ventricular extrasystoles); generally asymptomatic and self-limiting. Congestive heart failure, dose-related. The relative cardiotoxicity of idarubicin compared to doxorubicin is unclear. Some investigators report no increase in cardiac toxicity at cumulative oral idarubicin doses up to 540 mg/m^2; other reports suggest a maximum cumulative intravenous dose of 150 mg/m^2. Other cardiovascular side effects include arrhythmias, chest pain, and myocardial infarction.

Central nervous system: Headache

Dermatologic: Alopecia (25% to 30%), radiation recall, skin rash (11%), urticaria

Oral: mucositis 10-20%

Gastrointestinal: Nausea, vomiting (30% to 60%); diarrhea (9% to 22%); stomatitis (11%); GI hemorrhage (30%)

Genitourinary: Discoloration of urine (darker yellow)

Hematologic: Myelosuppression, primarily leukopenia; thrombocytopenia and anemia. Nadir: 10-15 days Recovery: 21-28 days

Hepatic: Elevations of bilirubin and transaminases (44%) 1% to 10%:

Central nervous system: Seizures

Neuromuscular & skeletal: Peripheral neuropathy <1%: Hyperuricemia

Overdosage/Toxicology: Symptoms of overdose include severe myelosuppression and increased GI toxicity. Treatment is supportive. It is unlikely that therapeutic efficacy or toxicity would be altered by conventional peritoneal or hemodialysis.

Drug Interactions: Patients may experience impaired immune response to vaccines; possible infection after administration of live vaccines in patients receiving immunosuppressants

Stability: Store intact vials of solution under refrigeration (2°C to 8°C/36°F to 46°F); protect from light. Solutions diluted in D5W or NS for infusion are stable for 4 weeks at room temperature and 7 days under refrigeration.

Mechanism of Action: Similar to doxorubicin and daunorubicin; inhibition of DNA and RNA synthesis by intercalation between DNA base pairs

Pharmacodynamics/Kinetics: Absorption: Oral: Variable (4% to 77%; mean: ~30%)

Distribution: Vd: 64 L/kg (some reports indicate 2250 L)

Metabolism: Hepatic to idarubicinol (pharmacologically active)

Half-life elimination: Oral: 14-35 hours; I.V.: 12-27 hours Time to peak, serum: 1-5 hours

Excretion: Oral: Urine (~5% of dose; 0.5% to 0.7% as unchanged drug, 4% as idarubicinol); hepatic (8%)

I.V.: Urine (13% as idarubicinol, 3% as unchanged drug); hepatic (17%)

Dosage: Refer to individual protocols.

I.V.: Leukemia induction: 12 mg/m^2/day for 3 days  
Leukemia consolidation: 4-8 mg/m/day for 2 days

Extravasation management: Topical cooling may be achieved using ice packs or cooling with circulating ice water. Cooling of site for 24 hours as tolerated by the patient. Elevate and rest extremity 24-48 hours, then resume normal activity as tolerated. Application of cold inhibits vesicant's cytotoxicity. Application of heat can be harmful and is contraindicated. If pain, erythema, and/or swelling persist beyond 48 hours, refer patient immediately to plastic surgeon for consultation and possible debridement.

